5.4 Initial SUBLOCADE Dosing Criteria

In order to initiate SUBLOCADE dosing the following criteria must be met:

- 1) Clinically stable (respiratory rate [RR] ≥ 12 , pulse oximetry $> 95\%$, Glasgow Coma Scale [GCS] score of 15)
- 2) No allergic reaction or hypersensitivity to SUBOXONE sublingual film.
- 3) More than 8 hours after the last dose of short acting opioid other than the SUBOXONE dose administered in the ED or at the clinic, or more than 48-72 after last dose of methadone.

6 STUDY CONDUCT

6.1 Subject Enrolment

Study participation begins once written informed consent is obtained; a subject ID is then assigned. The subject ID will be used to identify the subject during the screening process and throughout study participation, if applicable.

The Investigator is responsible for maintaining a master list (i.e., a subject identification list) of all consented subjects and will document all subjects that did not meet study eligibility criteria (i.e., screen failures), including reason(s) for ineligibility (i.e., a subject screening and enrolment log). Ineligible subjects, as defined by the protocol-specific inclusion and exclusion criteria, should not receive SUBLOCADE and should be documented as screen failures.

Controls will be selected from OD ED VCU visits beginning in 2015. The dataset will be anonymized; therefore, consent is not required and will not be obtained.

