
Rationale: Individuals with opioid use disorder (OUD) who overdose (OD) on opioids have a high risk of repeat opioid OD. At the Virginia Commonwealth University (VCU) Medical Center, emergency department (ED) data between 2015 and the end of 2017 indicate that, on average, 27% of individuals seen for an index opioid OD in the ED had a second event (OD or death due to opioid OD). Seventy percent of these events occurred within the first 6 months following the index episode with the majority occurring in the first 2 months post initial OD. Most likely due to the prevalence of fentanyl and fentanyl derivatives in heroin, the risk of fatality with opioid OD has risen exponentially in the United States (US) over the last several years (Mercado 2014).
 
Treatment of OUD patients at high risk of OD (such as when released from incarceration), with methadone or buprenorphine reduces the risk of OD index cases by up to 85% (Marsden 2017). This study will assess whether OUD patients treated with SUBLOCADE™ (buprenorphine extended-release injection for subcutaneous use) in the ED, inpatient unit, or at the clinic within 7 days (168 h) of overdose after receiving a test dose of SUBOXONE® (buprenorphine and naloxone) following OD reversal with an opioid antagonist reduces subsequent opioid OD events (repeat OD and/or repeat OD with fatality) as compared to a historical control cohort and concurrent controls who decline treatment participation. The study will also provide data on feasibility of initiation of SUBLOCADE within 7 days (168 h) of an overdose and data on subsequent outpatient treatment engagement.

Target Population: Adults with moderate to severe OUD (as defined by DSM-5 criteria) following an opioid OD, received treatment with an opioid antagonist, and are clinically stable for a screening interview.

Number of Subjects: 100

Duration of Treatment: The total duration of study participation will be approximately 7 months. Subjects will receive treatment for approximately 6 months with an End of Treatment (EOT) visit at 7 months post treatment initiation.

Objective(s): The primary objective of this study is:
 
 Determine the effect of SUBLOCADE treatment in the ED, inpatient unit or in the clinic within 7 days (168 h) after opioid OD on repeat OD and death compared to a historical control group and concurrent controls who decline treatment participation.

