2.3 Exploratory

The exploratory objectives of this study are:

- To determine the effect of SUBLOCADE administered in the ED, inpatient unit or in the clinic within 7 days (168 h) of an opioid OD followed by SUBLOCADE administration monthly on the amount of opioid craving.
- To determine the efficacy of SUBLOCADE administered in the ED, inpatient unit or in the clinic within 7 days (168 h) of an opioid OD followed by SUBLOCADE in the clinic on opioid use as determined by Urine Drug Screen (UDS).
- To evaluate the effect of SUBLOCADE administered in the ED, inpatient unit or in the clinic within 7 days (168 h) of an opioid OD followed by SUBLOCADE in the clinic in the clinic on decision making using a delay discounting task and a brief opioid demand measure to measure craving valuation (hypothetical maximum price participants would be willing to pay for access to opioid, assessing craving/valuation).
- To evaluate the association between participant genetic polymorphisms and subjects with history of OD in subjects that consent to the PGx sub-study.
- To evaluate the relationship between genetics/behavioural laboratory measures of decision making and treatment outcome, including repeat OD in subjects that consent to the PGx sub-study.
- To determine the relationship between decision making and treatment retention and illicit opioid use.
- To evaluate healthcare resource utilisation associated with either treatment regimen as compared to the controls (2015-to end of data collection period) obtained from VCU anonymized health records.
- To assess the impact SUBLOCADE administered in the ED, inpatient unit or in the clinic within 7 days (168 h) of an opioid OD followed by administration of SUBLOCADE in

the clinic on treatment effectiveness as measured by Treatment Effectiveness Assessment (TEA), on medication satisfaction as measured by the Medication Satisfaction Questionnaire (MSQ), and on employment, presentism and absenteeism as assessed by the Work Productivity and Activity Impairment Questionnaire: Specific Health Problem (WPAI:SHP).

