3.3 Exploratory

The exploratory endpoints of this study are:

- Opioid craving in subjects as measured by Craving Visual Analog Scale (VAS) scores.
- Illicit opioid use as measured by urine drug screen (UDS) results.
- Genetic predictors of treatment response and OD.
- Predictability of treatment response based on impulse control as measured by decision making in the delay discounting task, and opioid cravings/valuation as measured by the brief opioid demand task.
- Numbers of ED and hospital visits compared to the historical control (2015-2018) obtained from VCU anonymized health records.
- Scores on Treatment Effectiveness Assessment (TEA), medication satisfaction as measured by the Medication Satisfaction Questionnaire (MSQ), and employment, presentism and absenteeism as assessed by the Work Productivity and Activity Impairment Questionnaire: Specific Health Problem (WPAI:SHP).

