14.2 Sample Size

The study will be powered based upon the primary endpoint, repeat opioid OD and death compared to historical and concurrent control data.

Rationale for sample size: Power calculations: sample size was calculated based on a primary outcome measure of reduced repeat opioid OD rates. Previous research has shown self-reported repeat lifetime OD rates of 15-23% for patients who were seen for an opioid OD (Morizio, Baum et al. 2017).

Based on VCU health system data, for patients seen in the ED for an opioid OD in 2016, 11.5% of those patients were either seen again in the ED for an opioid OD or had died based on Virginia Department of Health death registry data within 6 months after their initial ED visit. Based on power calculations below, with a 3% repeat OD or death rate for the novel treatment group vs. the 11.5% treatment as usual rate in the historical control group, with 99 participants in the novel treatment group and 198 participants in the historical control group there will be a power of 80% at a type I error rate of 5%. See table below. If there is a less than 3% repeat OD rate in the intervention group there will be greater than 80% power.

Fixed Power of 0.80 and sample size for equivalent or non-equivalent numbers of participants per group (intervention vs. historical treatment as usual)

repeated OD/death rate	Stat method	n1:n2 (1:1, 2:1 or :1 ratio)		
11.5% vs 2%	Z-test	86:86	117:59	148:49
	Nonparametric	94:94	148:74	198:66
11.5% vs 3%	Z-test	115:115	160:80	204:68
	Nonparametric	131:131	198:99	265:88

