14.7 Efficacy Analysis

14.7.1 Primary Efficacy Analysis

The repeat opioid OD or opioid-related death primary endpoint analysis will be performed using Cox proportional regression and compare the SUBLOCADE treatment arm to historical and concurrent control data. Propensity scores will be used to match study participants to controls. Repeat OD and deaths (measured as time-to-event or censored at 6 months post index OD) will be tracked using subject reports, electronic medical records and state death registries. Events will be counted within the 6 months of treatment period for all treated subjects.

Propensity score analysis will be used in the analysis of SUBLOCADE vs. the control for time to repeat OD or opioid-related death. Study subjects will receive a propensity score that will be matched to propensity scores in the control data. The propensity score, p , will also be used as a weight in the Cox proportional hazards model. All SUBLOCADE treatment group subjects will have a weight of $p=1$ and patients in the control groups will be weighted by $p/(1-p)$. Here p can be viewed as the probability that the control subject would have been a study participant if the study were performed during their treatment.

The propensity score will be estimated by fitting a logistic regression on a dataset consisting of the consenting subjects (subjects in the SUBLOCADE arm at VCU) and the controls. The response variable will be consent to treatment; predictors will include baseline characteristics such as subject age, gender, county, race and insurance status. This model will be used to generate the predicted probability of consent to participate among the controls.

The Cox proportional hazards model will use the controls as the reference group and code the SUBLOCADE arm as a factor variable. The analysis will test the coefficient for the SUBLOCADE arm versus the controls from the Cox regression, with the interpretation of the exponential (coefficient) as the hazard ratio for time to repeat OD or opioid-related death in subjects consenting to the active treatment group versus the control cohorts.

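### The primary hazard ratio pools controls from 2015 onward in one reference group, with no term for index-overdose date or control type, so any change in background risk over time is absorbed into the treatment effect

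*Combined protocol and SAP*

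**What the plan says.** **Control source.** Protocol 6.1: "Controls will be selected from OD ED VCU visits beginning in 2015". No end date is given there, and 13.1.1 also only gives 2015 as the start.

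**Control window elsewhere.** The healthcare-use endpoint in 3.3 is "compared to the historical control (2015-2018) obtained from VCU anonymized health records", and the Synopsis uses the same years. The matching objective in 2.3 reads "as compared to the controls (2015-to end of data collection period".

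**Primary model.** Section 14.7.1 fits a Cox model with the SUBLOCADE arm as a factor and the controls, historical and concurrent together, as the reference. Controls are weighted by p/(1-p). For the propensity model, "predictors will include baseline characteristics such as subject age, gender, county, race and insurance status". The Synopsis adds route of administration and comorbid substance use disorder to the Cox model. Calendar date, era and control type are not named as a covariate, matching variable, stratum or sensitivity analysis.

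**Background risk.** The Synopsis rationale says that "the risk of fatality with opioid OD has risen exponentially in the United States (US) over the last several years". It also reports that 27% of VCU patients in 2015 to 2017 had a second event, and that "Seventy percent of these events occurred within the first 6 months following the index episode". Section 14.2 plans on a different VCU figure, for 2016: "11.5% of those patients were either seen again in the ED for an opioid OD or had died", within 6 months.

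**Concurrent controls.** Patients who decline are followed passively for 24 weeks (study schematics), and a further comparison with them is listed under the primary endpoint (3.1).

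**The concern.** With non-randomised controls drawn from earlier years, the treatment indicator is partly an indicator of era. Balancing age, gender, county, race and insurance does not remove a change in drug supply or in usual care. Route of administration and comorbid substance use do not do so either. Opioid-related death is part of the primary endpoint, and the protocol itself says that overdose was becoming more lethal, so stability over time cannot simply be assumed.

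The direction is not known. A higher background risk during accrual than in the control years would hide a benefit. A lower one would create an apparent benefit. The comparison of ED and hospital visits with historical records (3.3) has the same weakness.

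**Working it through.** **Inputs.** From 14.2: 99 treated, 198 historical controls, 11.5% control risk, 3% treated risk, power 80%, type I error 5% (sidedness not stated). From the Synopsis: 27% with a second event, 70% of these within 6 months. Assumed, because the documents do not give it: the untreated risk during accrual, taken as either 11.5% or 18.9%.

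**1. The plan's own figure.** Exact power of Fisher's test, 99 vs 198, 3% vs 11.5%: 80.3% one-sided at 5%, which reproduces the stated 80%. The two-sided version gives 73.0%. The illustrations below therefore use one-sided 5%.

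**2. The two VCU rates.**
- 2015 to 2017: 0.27 × 0.70 = 0.189, or 18.9% by 6 months.
- 2016: 11.5%.
- Ratio: 18.9 / 11.5 = 1.64.

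**3. Is the gap a time trend?** The year 2016 lies inside 2015 to 2017. With equal-sized years and identical definitions, the other two years would average (3 × 18.9 − 11.5) / 2 = 22.6%. A steady rise or fall through 2016 would need one outer year at or above 3 × 18.9 − 2 × 11.5 = 33.7%. The death wording also differs (opioid-overdose death in the Synopsis, any death as worded in 14.2), and the follow-up behind the 27% is not stated. The gap therefore shows an unsettled control rate and does not establish drift.

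**4. No drug effect, risk falling between eras.** Treated risk 11.5%, historical controls 18.9%. Apparent hazard ratio with no concurrent controls: ln(1 − 0.115) / ln(1 − 0.189) = 0.58. With a share f of the 198 controls drawn from the accrual era, the control risk is f × 11.5% + (1 − f) × 18.9%.

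| Concurrent share | Control risk | Apparent HR | Chance of a result favouring SUBLOCADE |
|---|---|---|---|
| 0% | 18.9% | 0.58 | 44% |
| 25% | 17.05% | 0.65 | 29% |
| 50% | 15.2% | 0.74 | 17% |
| 75% | 13.35% | 0.85 | 8% |
| 100% (no drift) | 11.5% | 1.00 | 3.3% |

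**5. Real effect, risk rising between eras.** Accrual-era untreated risk 18.9%, historical controls 11.5%. Keeping the planned relative risk, treated risk = 18.9% × 3 / 11.5 = 4.9%. Power against controls at 11.5% is 53%. Keeping the planned hazard ratio instead gives a treated risk of 5.1% and power of 50%.

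**6. Information available.** Expected events at the planning rates: 99 × 0.03 + 198 × 0.115 = 3.0 + 22.8, about 26. This limits how many calendar terms a model can carry.

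Steps 4 and 5 use unweighted proportions, not the planned weighted Cox model.

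**The case against.** Four points can be made for the plan.

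- A reader might infer that the protocol admits that repeat-overdose risk was changing fast. It does not. The rationale speaks of the fatality of an overdose in the US as a whole and gives no trend in repeat overdose at VCU. This objection stands.
- A reader might take the 1.64-fold gap as measured drift. For the reasons in step 3 of the working, it is not. This stands too, although the death wording alone would not explain the gap: the lower figure carries the broader wording.
- A reader might conclude that drift cannot be told from drug effect at all. That goes too far. Same-era decliners are among the controls, and a separate comparison with them is planned. The protection is only partial: decliners select themselves, their number is not planned, and the primary model does not separate them from historical controls. The 44% is the extreme case without accrual-era controls.
- The propensity list is open-ended and covariate balance will be checked. Still, nothing commits the analysis to calendar time, and the balance check covers observed baseline characteristics.

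On the window, 2015 to 2018 for historical controls is compatible with an open start in 2015 for all controls. The clear clash is in the healthcare-use comparison: 2.3 against 3.3 and the Synopsis.

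**Conclusion.** The point holds as a gap in the primary analysis: if 14.7.1 is followed as written, the pooled hazard ratio mixes the drug effect with any change in background risk since 2015. Drift itself is possible but not demonstrated.

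If the two VCU rates bracket the truth, the chance of a false claim of superiority rises from 3.3% to 17% with half the controls concurrent, and to 44% with none. Drift in the other direction lowers power from 80% to roughly 50 to 53%. These sizes assume that the whole gap between the two rates is drift, that the test is one-sided at 5%, and that weighting does not alter the contrast. If part of the gap is a matter of definition, the distortion is smaller. The pooled result should not carry the causal conclusion alone.

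**What to change.** In 6.1 and 14.7.1:

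1. State one control window, with start and end, for historical and for concurrent controls. Use it throughout, including the ED and hospital-visit comparison (Synopsis, 2.3, 3.3).
2. Recompute the 6-month control rate by calendar period under the primary endpoint definition, and reconcile 11.5% with 18.9%.
3. Report the weighted hazard ratio against historical controls and against concurrent controls separately, as well as pooled.
4. Add a sensitivity analysis with a single linear term for index-overdose date, or a term for control type. State that pre-accrual years contain no treated subjects, so the adjustment relies on the trend among controls. If the historical and concurrent hazard ratios differ in direction, limit the causal conclusion accordingly.

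With about 26 expected events, a spline or half-year terms in the primary model would not be supportable, and none is asked for.

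**Cost.** SAP wording and extra analyses, with wider intervals for the separate and adjusted estimates. The anonymized extract must carry at least the year or half-year of the index overdose. Section 13.1.1 does not list a date among its contents, so this should be confirmed with the data provider.

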Upon ED discharge, patients will be instructed to use over the counter ibuprofen and acetaminophen as needed. They will also be provided with two oral doses of 50 mg of hydroxyzine as ancillary medications if needed in the judgement of the clinician. The subject will receive referral to an outpatient treatment clinic affiliated with the hospital system in which the ED resides.

Patients presenting to the ED for an opioid OD who received treatment with an opioid antagonist and who are not approached by the study team for enrollment (e.g. OD outside of regular business hours) will be given a referral card by a ED healthcare provider to go to the outpatient clinic for an initial screening visit. Subjects must arrive at the clinic within 7 days (168 h) of OD.

- 2) Patients presenting to the ED for an opioid OD who received treatment with an opioid antagonist and who are admitted to an inpatient unit will be approached regarding interest in study participation. Patients who are considered clinically stable and alert (respiratory rate [RR] \geq 12, pulse oximetry $>$ 95%, [GCS] score of 15), who deny recent/regular use of long-acting opioids (e.g. methadone) will be approached. Written informed consent will only be obtained if the patient's judgement is intact and there are no other serious underlying medical complications as determined clinically by the Investigator or a medically qualified sub-investigator or research nurse.

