5.2 Inclusion Criteria

Subjects must meet **all** of the following criteria:

1. Signed the informed consent form (ICF) and have the ability to comply with the requirements and restrictions listed therein.
2. Age: ≥ 18 years at time of executing the ICF.
3. Currently meets DSM-5 criteria for moderate to severe OUD.
4. Is clinically stable (respiratory rate [RR] ≥ 12 , pulse oximetry $> 95\%$, Glasgow Coma Scale [GCS] score of 15) and suitable for the trial in investigator's or designee's judgement.
5. Agrees not to take any buprenorphine products other than those administered during the current study throughout participation in the study.
6. Negative urine pregnancy test for females.
7. Vital signs (BP, HR, temperature) considered within normal limits or non-clinically significant elevation, as assessed by treating physician.

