5.3 Exclusion Criteria

A subject will not be eligible for inclusion in this study if any of the following criteria apply:

1. Current diagnosis, other than OUD, requiring chronic opioid treatment.
2. Active suicidal ideation in opinion of the Investigator or designee.
3. Female subject that is lactating, pregnant or planning to become pregnant during their participation in the study.
4. Uncontrolled intercurrent illness including, but not limited to, psychiatric illness/social situations that would limit compliance with study requirements or compromise the ability of the subject to provide written informed consent, signs of opioid toxicity more than 2 hours from naloxone administration or subjects with evidence of pulmonary edema.
5. Known allergy or hypersensitivity to SUBOXONE.
6. Any condition that, in the opinion of the Investigator would interfere with interpretation of subject safety or study results.

-
7. Currently receiving MAT for OUD (e.g. methadone, buprenorphine) or received methadone as a treatment for OUD within 30 days prior to consent.
 8. Concurrent treatment with another investigational agent.
 9. Concurrent enrolment in another clinical study, or observational study that includes MAT.
 10. Treatment for OUD required by court order.
 11. Current or pending incarceration/ legal action that could affect participation or compliance in the study.
 12. Subjects who are unable, in the opinion of the Investigator, to comply fully with the study requirements.
 13. Less than 48-72 hours since last use of long acting opioids (e.g., methadone), by self-report.
 14. Current intoxication with benzodiazepines or alcohol.
 15. Meet current DSM-5 diagnosis for severe Benzodiazepine or Alcohol Use Disorder, or endorse benzodiazepine or alcohol withdrawal symptoms.
 16. Current illicit opioid users who endorse regular use of long acting opioids (e.g. methadone).
 17. Total bilirubin $\geq 1.5x$ the upper limit of normal (ULN), alanine aminotransferase (ALT) $\geq 3xULN$, aspartate aminotransferase (AST) $\geq 3xULN$, serum creatinine $> 2xULN$, international normalized ratio (INR) $> 1.5xULN$
 18. Patients with a history of Long QT Syndrome or an immediate family member with this condition or those taking Class IA antiarrhythmic medications (e.g., quinidine, procainamide, disopyramide) or Class III antiarrhythmic medications (e.g., sotalol, amiodarone) or other medications that prolong the QT interval.

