13.1.1 Historical and Concurrent Control Data

The historical and concurrent control data used for exploratory OD comparison analyses will be provided by Virginia Commonwealth University as an anonymized data extract from their electronic medical record system beginning in 2015. Data will include, but not be limited to; demographics, discharge diagnoses and status and ICD 9/10 codes.

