14.4 Analysis Populations

14.4.1 Treatment Population

The Treatment Population includes all subjects who receive at least 1 dose of study medication. This population will be used for all safety and efficacy analyses. In the safety analyses, subjects will be analysed according to treatment actually received.

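### Controls have no eligibility rule, so patients who could not have enrolled carry weight in the primary comparison

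*Combined protocol and SAP*

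**What the plan says.** **Treated side.** Section 5.2 requires age 18 or over, clinical stability (respiratory rate, oximetry, GCS) and OUD: "Currently meets DSM-5 criteria for moderate to severe OUD". Section 5.3 excludes "Currently receiving MAT for OUD (e.g. methadone, buprenorphine) or received methadone as a treatment for OUD within 30 days prior to consent", pregnancy or lactation, and severe alcohol or benzodiazepine use disorder. Section 5.4 repeats the stability check before the injection. Section 14.4.1 then conditions on dosing: "The Treatment Population includes all subjects who receive at least 1 dose of study medication". Entry may come late. For patients sent to the clinic, the synopsis says "Subjects must arrive at the clinic within 7 days (168 h) of OD".

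**Control side.** Section 6.1 gives the only selection rule: "Controls will be selected from OD ED VCU visits beginning in 2015". Section 13.1.1 describes an anonymized extract: "Data will include, but not be limited to; demographics, discharge diagnoses and status and ICD 9/10 codes". Neither section attaches an inclusion or exclusion criterion. Section 2.3 (resource-use objective) describes controls from 2015 to the end of data collection. The synopsis and section 3.1 define concurrent controls as patients who decline.

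**Adjustment.** Section 14.7.1 matches on a propensity score and weights controls by p/(1-p). The model names age, gender, county, race and insurance status as examples of predictors. The synopsis adds route of administration and comorbid substance use disorder to the Cox model; section 14.7.1 does not repeat them. Balance diagnostics are planned on the observed baseline characteristics.

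**The concern.** The treated arm is filtered on disease severity, current treatment, physiological recovery and actual dosing. The control rule has no matching filter. A patient with no OUD, a patient already on MAT, or a patient who dies or overdoses again before anyone could have dosed them may enter the control group and receive a positive weight.

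Section 14.7.1 reads p as the probability that a control would have taken part. For an ineligible patient the protocol makes that probability zero, but a model that does not contain the eligibility variables will still return a positive value. Balance on age, gender, county, race and insurance would not reveal the problem.

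This comparison is the primary endpoint. The hazard ratio could therefore mix the effect of SUBLOCADE with the effect of being eligible.

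**Working it through.** **Step 1. Set the criteria side by side.**

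| Criterion | Treated | Control rule (6.1, 13.1.1) | Named in adjustment (14.7.1, synopsis) |
|---|---|---|---|
| Age 18 or over | required | not stated | age as a predictor only |
| Moderate to severe OUD | required | not stated | no |
| Not on MAT | required | not stated | no |
| No severe alcohol or benzodiazepine disorder | required | not stated | comorbid SUD, synopsis only |
| Stable, alive and dosed | required | not stated | no |

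**Step 2. Reproduce the plan's power.** Inputs from section 14.2: 3% of 99 treated versus 11.5% of 198 controls, 5% type I error, sidedness not given. The method is the exact power of Fisher's test: sum the binomial probabilities Bin(x; 99, 0.03) × Bin(y; 198, 0.115) over all outcomes whose hypergeometric lower-tail p-value is at most 0.05. The result is 80.25%, so the stated 80% reproduces as a one-sided test. Two-sided power is 73.0%.

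**Step 3. Mixed control group, no drug effect.** Let a share f of controls be ineligible, with r times the eligible rate. If the mixture shows 11.5%, the eligible rate is 11.5% / (1 - f + f·r). A drug with no effect then shows a crude risk ratio of eligible rate / 11.5%. Here f = 0.20 and both values of r are assumptions.

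- r = 2: 11.5 / 1.2 = 9.58%; risk ratio 9.58 / 11.5 = 0.83.
- r = 0.5: 11.5 / 0.9 = 12.78%; risk ratio 12.78 / 11.5 = 1.11.

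With the treated rate kept at 3%, one-sided power against eligible controls is 61.5% in the first case and 88.5% in the second (two-sided 52.7% and 83.0%).

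**Step 4. Range of eligible-control rates.** The documents give no event rate for trial-eligible controls, so it is varied. All figures use the unadjusted Fisher test at 99:198, one-sided with two-sided in brackets.

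| Eligible rate | Power, treated 3% | Chance of wrongly favouring a null drug against 11.5% controls |
|---|---|---|
| 8% | 41.9% (34.0%) | 17.8% (12.0%) |
| 9% | 54.5% (45.8%) | 11.5% (7.3%) |
| 10% | 66.1% (57.5%) | 7.1% (4.3%) |
| 11.5% | 80.3% (73.0%) | 3.3% (1.8%) |
| 13.5% | 91.8% (87.3%) | 1.0% (0.5%) |

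The protocol's own figures already differ by cohort. The synopsis rationale implies 0.27 × 0.70 = 18.9% at six months for 2015 to 2017, against 11.5% for 2016 in section 14.2.

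**Step 5. Events before dosing.** Section 14.7.1 censors at six months from the index overdose but counts treated events within the treatment period. A death before the first injection cannot occur in the treated arm, and a repeat overdose before it is not counted there. Both count for a control. The synopsis says most second events fall in the first two months. For scale, assume half to five-sevenths (0.5 / 0.7) of the 11.5 points falls evenly over 61 days. The first seven days then hold 5.75 × 7/61 = 0.66 to 8.21 × 7/61 = 0.94 points. That is the exposure for a subject dosed on day 7. It is close to nil for one dosed in the ED on the day of the overdose.

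**The case against.** Much can be said for the plan. Section 6.1 names a source pool from which controls are selected, and selection then runs through propensity matching. Section 14.2 describes the historical group as patients seen for an opioid overdose. The predictor list is open-ended. These points stand, but none of them supplies a criterion for OUD, MAT or survival to entry.

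The two control groups also differ. Under the synopsis, patients are approached only when stable and denying use of long-acting opioids. Decliners who were approached have therefore passed part of the screen, and the problem is mainly one of historical controls. What remains is that nothing says how decliners are identified in an anonymized extract.

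Four stronger readings are tempting and are not supported:

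- That every overdose visit is a control by design, including minors and deaths at the index visit. This is inferred from silence.
- That enrolled subjects' own visits serve as controls. Concurrent controls are defined as decliners. The real gap is that no step removes enrolled subjects from an extract that may run to the end of data collection.
- That early events are impossible in the treated arm. Only events before dosing are outside it; a subject dosed in the ED can have a counted event soon afterwards.
- That the asymmetry as a whole flatters SUBLOCADE. The protocol itself cites a reduction in overdose risk of up to 85% with methadone or buprenorphine. MAT patients among the controls could therefore lower the control rate and bias against the drug.

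**Conclusion.** The concern holds. Following the plan as written allows patients who could not have enrolled to carry weight in the primary comparison, and the named adjustments do not cover the criteria that separate the groups. This is more than missing detail, because the p/(1-p) weight depends on every control having had a real chance of enrolment.

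One component has a known direction: events before dosing count only against controls and so favour SUBLOCADE. The net direction of the OUD and MAT differences is unknown. The crude null risk ratios of 0.83 and 1.11 illustrate a 20% ineligible share with twice or half the eligible rate; they are not estimates. All of the power and error figures use an unadjusted Fisher test with assumed eligible rates, not the weighted Cox model.

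**What to change.** Change sections 6.1, 13.1.1 and 14.7.1, and then 14.2:

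1. Restrict controls to patients aged 18 or over with an opioid-overdose visit and a coded OUD diagnosis.
2. Where the record holds the information, require antagonist treatment and exclude pregnancy, severe alcohol or sedative use disorder, and current MAT.
3. List the trial criteria that cannot be emulated, such as DSM-5 severity, GCS, respiratory rate and oximetry, and entry through EMS without an ED visit.
4. Set a time zero for each control that matches the treated subjects' time from overdose to first dose, and require the control to be alive and event-free at that point. A discharged-alive filter would not do: subjects can be dosed on the inpatient unit, so a treated death before discharge would count while the matching control was dropped.
5. Use one index overdose per patient. Have the data holder flag decliners and remove enrolled subjects before anonymizing.
6. Recompute the control rate and the power on this cohort, and state whether the 5% is one-sided.

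The cost is extract programming and a smaller control pool. Demographics, diagnoses, discharge status and ICD codes are listed in 13.1.1. Antagonist use and current MAT are not, so those filters may be only approximate or unavailable. The restated power may be less favourable.
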